11.2.3 Interim analysis

Interim analyses will be conducted after patient no. 1650 and 2500 has been followed for 90 days.

The DMSC will constitute its own plan of monitoring and meetings. The charter for the independent Data Monitoring and Safety Committee (DMSC) (*appendix 3*) defines the minimum of obligations and primary responsibilities of the DMSC as perceived by the SC, its relationship with other trial components, its membership, and the purpose and timing of its meetings.

The DMSC may recommend pausing or stopping the trial if group-difference in the primary outcome measure, SARs or SUSARs are found at the interim analyses with statistical significance levels adjusted according to the LanDeMets group sequential monitoring boundaries based on O'Brien Fleming alpha-spending function [69]. If an analysis of the interim data from 1650/2500 patients fulfils the LanDeMets stopping criterion the inclusion of further patients will be paused and an analysis including patients randomised during the analysis period will be performed. If this second analysis also fulfils the LanDeMets stopping criterion according to the group sequential monitoring boundaries the SC may stop the trial [67]. Furthermore, the DMSC can recommend pausing or stopping the trial if continued conduct of the trial clearly compromises patient safety. However, stopping for futility to show an intervention effect of 15% RRR will not be an option as intervention effects less than 15% RRR of all-cause mortality may be clinically relevant as well.

11.2.4 Early stopping criteria

See previous section

11.2.5 Accountability procedure for missing data/population for analysis

If less than 5% of data are missing on any primary or secondary outcome, a complete case analysis without input of missing values will be performed. If missing data are more than 5%, a blinded statistician will assess whether data are 'missing completely at random' (MCAR criterion) based on a rational assessment of the pattern of missing data [70]. Little's test will be used if there remains doubt [71]. If it is concluded that data are not 'missing completely at random', multiple imputation using chained equations will be performed by creating ten input data sets under the assumption that the data are missing data at random (MAR criterion) [72, 73]. We will use outcomes and the most important baseline characteristics in the multiple imputation. The exact variables to be used to estimate the missing values will be outlined in

the detailed statistical analysis plan: If multiple imputation is used, then the primary result of the trial will be based on these data. The unadjusted, non-imputed analysis will also be made available. If multiple imputation is used, we use a best-worst worst-best case scenario as a sensitivity analysis to assess the potential impact of any pattern of missingness including that the data are missing not at random (MNAR criterion) for the trial results. In the 'best-worst-case' scenario it is assumed that all patients lost to follow-up in the experimental group have had a beneficial outcome (e.g. have survived, had no serious adverse reactions etc.); and all those with missing outcomes in the control group have had a harmful outcome (e.g. have not survived; have had a serious adverse reaction etc.). Conversely, in the 'worst-best-case' scenario, it is assumed that all patients who were lost to follow up in the experimental group have had a harmful outcome; and that all those lost to follow-up in the control group have had a beneficial outcome. When continuous outcomes are used, a 'beneficial outcome' will be defined as the group mean plus two standard deviations (SD) of the group mean, and a 'harmful outcome' will be defined as the group mean minus two SD of the group mean.

12. Quality control and quality assurance

The coordinating investigator will be responsible for organizing the trial sites including education of local investigators, research nurses, and other trial site personnel before the initiation of the trial. This education will be continuously documented and two annual investigator meetings will be planned.

After initiation, trial site investigators will be responsible for all trial-related procedures at their site, including education of staff in trial-related procedures, recruitment and follow-up of patients and entry of data. Clinical staff at the trial sites will be responsible for the treatment of trial patients.

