Proportions of patients with clinically important GI bleeding: proportion of patients with one or more episodes of clinically important GI bleeding as defined above

Proportion of patients with one or more infectious adverse events: proportion of patients with one or more episodes of pneumonia or CDI

1-year mortality: landmark mortality 1 year post-randomisation

Duration of life support in the ICU: the number of days alive and free from respiratory or circulatory support and of renal replacement therapy as defined below. The outcome will be days alive without use of mechanical ventilation, circulatory support or renal replacement therapy in the 90-day period, and will be defined as the percentage of days without mechanical ventilation, circulatory support and renal replacement therapy (as defined in daily collected variables) in the 90 days after randomisation

Serious adverse reactions: number of serious adverse reactions as defined below

The elements of all composite outcomes will be reported in the supplementary material

A health economic analysis will be performed. The analytic details will be based on the result of the trial and specified (cost-benefit vs cost-minimisation analyses).

Definitions of serious adverse reactions

A serious adverse reaction (SAR) is defined as any adverse reaction that results in death, is life-threatening, requires hospitalization or prolongation of existing hospitalization, or results in persistent or significant disability or incapacity.

Patients will be monitored for onset of SARs occurring between the first dose of trial medication and until discharge from the ICU. If a patient is withdrawn from the trial intervention, SARs will be recorded for 24 hours after the last dose of trial medication or discharge from ICU. If the patient is readmitted to the ICU and trial intervention is reintroduced, data collection for SARs will be resumed. If a patient experiences a SAR the patient will be withdrawn from the trial intervention but data collection and follow-up will be continued (see section 4.3.2)

SARs will be defined as follows:

Anaphylactic reactions defined as urticaria and at least one of the following

- Worsened circulation (>20% decrease in blood pressure or >20% increase in vasopressor dose)
- Increased airway resistance (>20% increase in the peak pressure on the ventilation)
- Clinical stridor or bronchospasm
- Subsequent treatment with bronchodilators

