Because of the widespread use of SUP, no reliable control group for sample size estimation is available and producing reliable sample size estimations according to anticipated effects on GI bleeding is difficult.¹ As a consequence it has been necessary to calculate sample size estimations given that something may change if we withhold PPI until GI bleeding actually happens. Assuming a baseline 90-day mortality of 25%,² $\alpha=0.05$ (two-sided), and $\beta=0.1$, 3350 patients (2 x 1675) will be needed to show a 20% relative risk reduction (RRR) or increase (RRI) corresponding to a 5% absolute risk reduction or increase in the primary outcome measure. Trial Sequential Analysis^{22,23} of existing trials (n=16) has showed that 35% (1584 patients) of the required information size to

detect or reject a 20% RRR or RRI corresponding to 4575 patients has been accrued.⁸

Consequently, there is at least an information gap of around 3000 patients taking a 20% RRR in mortality as a clinically relevant effect size.

Outcome measures

Primary outcome

The primary outcome measure is all-cause mortality within 90 days after randomisation.

Secondary outcomes

1. Proportion of patients with one or more episodes of clinically important GI bleeding, pneumonia, *Clostridium difficile* infection or myocardial ischemia. The events are defined in appendix 1
2. Proportion of patients with one or more episodes of clinically important GI bleeding
3. Proportion of patients with one or more infectious adverse events (pneumonia or *Clostridium difficile* infections)
4. All-cause mortality within 1 year after randomisation
5. Percentage of days alive without use of life support (mechanical ventilation, circulatory support or renal replacement therapy) in the 90-day period
6. The number of patients with one or more serious adverse reactions (SARs) (defined in appendix 2)
7. A health economic analysis will be performed. The analytic details will be based on the result of the trial and specified prior to the analysis.

Pre-planned subgroup analyses

The primary outcome measure will be compared in the following pre-specified subgroups (definitions provided in appendix 2)

1. Shock at randomisation (y/n) (a hypothesised increased intervention effect in patients with shock at randomisation)
2. Mechanical ventilation at randomisation (y/n) (a hypothesised increased intervention effect in patients mechanically ventilated at randomisation)

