If multiple imputation is used, the primary result of the trial will be based on these data. A 'best-worst, worst-best case' scenario will be used as a sensitivity analysis to assess the potential impact of any pattern of missingness including that the data are missing not at random (MNAR criterion) for the trial results. In the 'best-worst-case' scenario it is assumed that all patients lost to follow-up in the experimental group have had a beneficial outcome (e.g. have survived) and all those with missing outcomes in the control group have had a harmful outcome (e.g. have not survived). Conversely, in the 'worst-best-case' scenario, it is assumed that all patients who were lost to follow up in the experimental group have had a harmful outcome; and that all those lost to follow-up in the control group have had a beneficial outcome.

The unadjusted, non-imputed analysis will also be presented.

General analytic principles

1. All main analyses will compare the two intervention groups in the intention-to-treat (ITT) population.²⁴⁻²⁶

The ITT population will be all patients randomised except:

- patients withdrawing consent for the use of data
- patients who were erroneously randomised AND who did not receive the trial intervention.²⁷

The conclusion of the trial will be based on the ITT analysis

2. In all analyses, a maximum level of 5% (two-sided) type 1 error will be regarded as statistically significant
3. Test-of-interaction will be applied for all subgroup analyses (logistic regression)

Statistical analyses

Trial profile

The flow of trial participants will be displayed in a Consolidated Standards of Reporting Trials (CONSORT) diagram. The number of participants fulfilling the inclusion criteria, the number of excluded participants and reasons for exclusion, and the number of participants included in the final analyses will be presented.

Primary outcome measure

The primary analysis will be a logistic regression analysis adjusted for stratification variables (site and presence of haematological cancer, y/n) of the ITT population. Results will be presented as odds ratios and relative risk ratios (relative risk ratios computed from odds ratios with covariates set to mean values for numeric covariates and the largest group for categorical).

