The secondary analysis will be a multiple logistic regression analysis of the ITT population adjusted for stratification variables and additionally differences in potential confounders: age, SOFA score at baseline, and type of admission (medical, elective surgery or emergency surgery). Intervention group and the stratification variable haematological cancer are regarded as fixed effects and trial site is regarded as random effects in the model. Furthermore, frequencies and percentages per group will be reported and an unadjusted Chi-square test for differences in the primary outcome will be provided.

Pre-defined subgroup analyses (see former section) of the ITT population will be conducted using logistic regression analysis adjusted for stratification variables.

A sensitivity analysis of the primary outcome measure including the per-protocol population will be conducted. The per-protocol population will be all randomised patients except those having one or more protocol violations defined as:

- Patients who did not receive the allocated trial intervention at all
- Patients who did not receive the trial intervention for at least two days in a row
- Patients who received treatment (open label) with PPI or histamine-2-receptor antagonists except for those receiving it according to the protocol (i.e. occurrence of GI bleeding after randomisation).
- Patients who withdrew from trial intervention, but consented to the use of data
- Monitoring revealed that one or more in- or exclusion criteria were violated

Secondary outcome measures

The secondary outcomes will only be analysed in the ITT population. The primary analysis of the binary secondary outcome measures will be a logistic regression analysis adjusted for the stratification variables (site and presence of haematological cancer). Results will be presented as odds ratios and relative risk ratios.

Furthermore, frequencies and percentages per group will be reported and an unadjusted Chi-square test for differences in the primary outcome will be provided.

The primary analysis of rate data ('Percentage of days alive without life support in the 90-day period') will be a generalized linear model (initially Poisson distribution, alternatively negative binomial).²⁸ If the assumptions for Poisson distribution or negative binomial distribution are not met, data will be analysed using the non-parametric Van Elteren test adjusted for site, but no other variables.²⁹

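### For the percentage of days alive without life support, the protocol's mean ± 2 SD rule gives a best case above 100%, or on its other reading no bound at all, and the SAP sets no values in its place

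*Combined protocol and SAP*

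**What the plan says.** Protocol section 11.2.5 makes the extreme-case analysis conditional: "If multiple imputation is used, we use a best-worst worst-best case scenario as a sensitivity analysis". For binary outcomes it uses the true extremes, with every missing patient counted as a success in one arm and a failure in the other. For continuous outcomes a beneficial value "will be defined as the group mean plus two standard deviations (SD) of the group mean" and a harmful value "will be defined as the group mean minus two SD of the group mean". No truncation is stated.

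The outcome concerned is the life-support outcome. Appendix 4 of the protocol says it "will be defined as the percentage of days without mechanical ventilation, circulatory support and renal replacement therapy" over the 90 days after randomisation. The SAP lists it as "Percentage of days alive without use of life support (mechanical ventilation, circulatory support or renal replacement therapy) in the 90-day period". Either way it cannot leave 0 to 100. Under Secondary outcome measures, the SAP says its primary analysis "will be a generalized linear model (initially Poisson distribution, alternatively negative binomial"), with the Van Elteren rank test as fallback.

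The SAP's Missing data section restates the best-worst and worst-best scenario. Its example is survival: "all patients lost to follow-up in the experimental group have had a beneficial outcome (e.g. have survived"). It neither repeats the mean ± 2 SD sentence nor replaces it.

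**The concern.** An extreme-case analysis should show how far the result could move if the missing data were as favourable or as unfavourable as they can be. Two standard deviations from the mean can do that roughly for a symmetric, unbounded measurement. This outcome is bounded and split in two: about a quarter of patients are expected to die and will mostly score low, while most survivors will score high. The mean is then nearer the top of the scale and the SD is large, so the upper value is likely to pass 100%.

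The wording has a second reading. The SD of a group mean is, strictly, its standard error, which is very small with about 1675 patients per group.

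This scenario is the plan's only check on data missing not at random for this outcome. On the first reading it can give patients more support-free days than the window holds. On the second it would give reassurance that has not been tested.

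**Working it through.** **Inputs from the documents.** 90-day mortality 25% and 1675 patients per group (protocol 11.1.1); scale 0 to 100 (Appendix 4 and SAP). There is no stated mean, SD or expected missingness for this outcome, so there is no figure of the plan's to reproduce on this point. The group size enters only as n for the standard error. It is itself reproducible: 25% versus 30%, two-sided 5%, 90% power, pooled variance and no continuity correction gives 1674 per group.

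**Step 1: when does the rule stay on the scale?** Mean + 2 SD ≤ 100 requires SD ≤ (100 − mean)/2. That is 15 at mean 70, 12.5 at mean 75 and 10 at mean 80. Mean − 2 SD ≥ 0 requires SD ≤ mean/2, which is 35 at mean 70.

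**Step 2: plausible mean and SD (assumed).** Let non-survivors average d, survivors average s, and the SD within each be w. Then mean = 0.25d + 0.75s and SD = √(0.25 × 0.75 × (s − d)² + w²).

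| d, s | w | Mean | SD | Mean + 2 SD | Mean − 2 SD |
|---|---|---|---|---|---|
| 5, 95 | 0 to 15 | 72.5 | 39.0 to 41.8 | 150 to 156 | −5 to −11 |
| 10, 92 | 0 to 15 | 71.5 | 35.5 to 38.5 | 143 to 149 | +0.5 to −6 |
| 20, 90 | 0 to 15 | 72.5 | 30.3 to 33.8 | 133 to 140 | +12 to +5 |
| 10, 85 | 0 to 15 | 66.3 | 32.5 to 35.8 | 131 to 138 | +1 to −5 |

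The upper value, 131% to 156%, corresponds to 0.90 × 131 = 118 up to 0.90 × 156 = 140 days in a 90-day window. With w = 0, 8 and 15 there are 12 cases. The lower value is at or above 0 in 5 of them.

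A wider grid (mortality 20% to 30.5%, d from 0 to 60, s from 80 to 95) gives an upper value above 100 in 353 of 360 cases. The 7 exceptions need non-survivors averaging 60% and w of 5 or less. The lower value is below 0 in 139 of 360.

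**Step 3: does the denominator matter?** Simulation with 25% mortality and lognormal durations (log-SD 1), with median life support 2 to 10 days and median time to death 8 to 20 days:

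- 90-day denominator: mean 67 to 75, SD 34 to 38, upper 135 to 151, lower −1.4 to +1.4.
- Days-alive denominator: mean 73 to 88, SD 24 to 30, upper 132 to 137, lower 13.5 to 40.

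The upper value is impossible in both. In the second, the lower value is possible but well above the true worst of 0.

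**Step 4: effect on the comparison.** With a fraction m missing in each arm and equal observed means and SDs, the rule moves the between-arm difference by m × 4 SD. The scale allows at most m × 100, so the rule overshoots when SD exceeds 25. At an assumed m = 6%:

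- SD 36: 0.06 × 4 × 36 = 8.6 points, against a maximum of 6.0.
- SD 23.5 to 29.7 (days-alive simulation): 5.6 to 7.1 points, against 6.0.

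**Step 5: standard-error reading.** SE = SD/√1675. For SD 20 to 40, 2 SE = 1.0 to 2.0 points. At m = 6% and SD 36 the shift is 0.06 × 4 × 36/√1675 = 0.2 points, which is close to mean imputation.

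**The case against.** The strongest objection is that the SAP governs the primary publication, rewrites the missing-data section and leaves the continuous-outcome sentence out. The omission may mean the rule was dropped. That is a fair reading, and the SAP does not settle it. But if the rule was dropped, this outcome has no best and worst values at all. On either reading the SAP needs a sentence.

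It can also be said that the SAP calls this outcome rate data rather than continuous, and that it is not the only candidate. The protocol counts serious adverse reactions, and of the economic work the SAP says "A health economic analysis will be performed", with details to follow, so cost data may come. That stands, and no claim is made here that the rule could apply to nothing else. The life-support percentage is the clinical outcome in the SAP with a defined non-binary scale, and no other values are given for it.

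A reader might infer that both values always fall off the scale and that the analysis would fail to run. The documents do not support that. They give no mean or SD, the lower value is often at or above 0, and only a negative value defeats the Poisson or negative binomial model. Under the rank-test fallback, how far a value lies out of range has no effect, although a value above 100 would still rank above every real patient with a perfect score. Nor does the rule always exaggerate sensitivity, since that needs an SD above 25.

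**Conclusion.** The point holds within limits. Read as 2 SD of the observations, the rule will almost certainly assign a best case above 100%: about 131% to 156% on the assumptions shown, where 25% mortality is the plan's figure and the survivor and non-survivor means and spreads are assumed. The worst case may fall slightly below 0 or may stop short of the true worst, depending on the spread and on whether the denominator is 90 days or days alive. Read as the standard error, the values are about 1 to 2 points from the mean and bound nothing. The text does not say which reading is meant.

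The rule operates only if more than 5% of data are missing and multiple imputation is used; the protocol also requires a judgement that data are not missing completely at random, a step the SAP omits. Some missingness is foreseeable, because the outcome rests on daily records, patients may withdraw from daily registration (4.3.1), and transferred patients are followed for secondary outcomes only as far as possible (4.3.2). No rate is stated, and the 6% used above is an assumption. The primary outcome and the trial's main conclusion do not depend on this. It should be corrected, as a matter of limited reach.

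**What to change.** Add to the SAP's Missing data section: for the percentage of days alive without life support, the beneficial value is 100% and the harmful value is 0%, in place of the protocol's mean ± 2 SD rule. Where a patient's days are partly observed, keep the observed days and any known date of death, and set only the unobserved days to free or not free of support. This follows the logic the plan already uses for binary outcomes.

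The scale-end version costs one sentence and needs no new data. The day-level version needs slight extra programming to rebuild patient-days and requires the denominator (90 days or days alive) to be stated. If the economic analysis brings in cost data, its own plan should say what applies there. The change is best made before the groups are unmasked.

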12.1 Monitoring of the intervention groups

The trial will be externally monitored following a monitoring plan developed in collaboration with the GCP Unit in Copenhagen, which will coordinate the monitoring done by local GCP units and/or monitors in all countries. A centralised day-to-day monitoring of the eCRF will be done by the coordinating investigator or her delegates.

13. Legal and organisational aspects

13.1 Finance

13.1.1 Trial funding

The SUP-ICU trial is funded by the Innovation Fund Denmark (4108-00011A). The funding sources will have no influence on trial design, trial conduct, data handling, data analysis or publication.

13.1.2 Compensation

Trial sites will be given DKR 1500 (200 EUR) in case money for each patient with 90-day follow-up to compensate for the increased workload participation infers.

